## 11. MEASUREMENT OF EFFECT

### 11.1.1 Definitions

**Evaluable for toxicity:** All participants who receive at least one dose of study treatment will be evaluable for toxicity from the time of their first treatment.

**Evaluable for objective response:** Only those participants who have measurable disease present at baseline, have received at least one cycle of therapy, and have had their disease re-evaluated will be considered evaluable for response. These participants will have their response classified according to the definitions stated below. (Note: Participants who exhibit objective disease progression or die prior to the end of cycle 1 will also be considered evaluable.)

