## 13.2 Sample Size, Accrual Rate and Study Duration

A maximum of 18 patients will be accrued for the phase I study.

A maximum of 20 evaluable patients will be accrued for the phase II study. To be evaluable for response, patients must have one cycle of therapy. Patients inevaluable for response will be replaced. Assuming an H0 of major response rate of 50% vs. an H1 of 80%, a sample of 20 patients would have a power of 80% with an alpha of 0.04 to detect a difference. If 15 patients or more obtain a major response, then the study would be a success, if 14 patients or fewer obtain a major response, then the study would be a failure and the combination should not continue further evaluation. Sample size and power estimation were obtained using the binomial method (STATA version 13).

Accrual time will be approximately 12-18 months, at a rate of 2-3 patients per month. Patients will be followed for the duration of time on active protocol therapy (47 cycles), and then 2 additional years after completion of cycle 47. Participants will be followed for up to 24 months after completion of protocol therapy, or until termination from study, disease progression, initiation of new anti-neoplastic therapy, or death. Participants removed from protocol therapy for unacceptable adverse event(s) will be followed until resolution of the adverse event to at least grade 1 or less, or stabilization of the adverse event.

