### **13.7.2 Evaluation of the Primary Efficacy Endpoint**

All participants who have received at least one cycle of therapy are eligible for response assessment. Inevaluable patients for response will be replaced. All conclusions will be based on evaluable participants.

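### The one-cycle rule in 13.2 and 13.7.2 omits the exception in 11.1.1 for early progression and death, so a known non-responder can be replaced within the 20 to which the 15/14 rule applies

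*Combined protocol and SAP*

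**What the plan says.** Four places in the combined protocol and SAP bear on who counts.

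- **11.1.1 Definitions.** Evaluability for response needs measurable disease at baseline, at least one cycle of therapy and a disease re-evaluation. A note then adds an exception: "Participants who exhibit objective disease progression or die prior to the end of cycle 1 will also be considered evaluable".
- **13.2 Sample Size, Accrual Rate and Study Duration.** "A maximum of 20 evaluable patients will be accrued for the phase II study". Then: "To be evaluable for response, patients must have one cycle of therapy. Patients inevaluable for response will be replaced". The same paragraph holds the decision rule: "If 15 patients or more obtain a major response, then the study would be a success"; 14 or fewer is a failure. The exception is neither repeated nor cross-referenced.
- **13.7.2, on the primary efficacy endpoint.** The one-cycle condition and the replacement rule appear again here: "All participants who have received at least one cycle of therapy are eligible for response assessment. Inevaluable patients for response will be replaced". It then rests all conclusions on evaluable participants, again without the exception.
- **13.5 Analysis of Primary Endpoints.** The primary proportion with a major response is calculated in the full analysis set (FAS), meaning Phase II participants with at least one dose.

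Sections 1.1 and 5.1 record that Phase II was never opened.

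**The concern.** A participant who dies before completing Cycle 1 has a known outcome: 11.1.2 treats death from any cause as a progression event, and there can be no later major response. The 11.1.1 note keeps that participant in the count. The must in 13.2 takes the participant out and brings in someone who may respond.

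Such a swap can only leave the responder count unchanged or raise it. Because removal depends on a bad outcome, the 20 would be selected in favour of the treatment, and the 15/14 rule would be easier to pass than its stated error rate implies. Two analysts working from different sections could also reach opposite decisions from the same records.

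**Working it through.** **1. The definitions applied to three records**

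| Record | 11.1.1 with note | 13.2 and 13.7.2 as written |
|---|---|---|
| Dies after the Day 15 infusion and before the Day 22 infusion | Evaluable, non-responder | Has not had one cycle; replaced |
| Progresses during Cycle 1, continues and completes the cycle | Evaluable | Evaluable |
| Completes Cycle 1, then progresses in Cycle 2 without a response | Evaluable, non-responder | Evaluable, non-responder |

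Only the first kind of record (death, or progression with therapy stopped, before Cycle 1 is complete) is treated differently.

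**2. The decision can change.** Take 20 participants with 14 major responders, 5 other non-responders and 1 early death. Under 11.1.1 the result is 14/20, a failure. Under 13.2 the death is replaced, and if the replacement responds the result is 15/20, a success. Among all treated that success is 15/21 = 71.4%, with an exact 95% interval of 47.8% to 88.7%. The interval for 15/20 is 50.9% to 91.3%. So one replacement moves the lower limit from just above the 50% null to just below it.

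**3. The plan's own figures.** Inputs from 13.2: n = 20, success at 15 or more, null 50%, alternative 80%, and "a sample of 20 patients would have a power of 80% with an alpha of 0.04 to detect a difference". With X binomial:

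- Power: P(X ≥ 15 | 20, 0.80) = 0.804, matching the stated 80%.
- One-sided alpha: P(X ≥ 15 | 20, 0.50) = 0.0207. Doubled, this is 0.0414, which matches the stated 0.04 to two decimals. The plan does not state sidedness.

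**4. Effect of replacement.** Let e be the proportion who die, or progress and stop, before completing Cycle 1, all of them non-responders. The documents give no e for the combination, so it is an assumption. Suppose the 50% null refers to all treated participants. Replacement then conditions on getting through Cycle 1, and the response rate among the 20 retained becomes 0.50/(1 − e). The false-success probability is P(X ≥ 15 | 20, 0.50/(1 − e)), and the chance that at least one of 20 is affected is 1 − (1 − e)^20.

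| Assumed e | Rate among the 20 | False success, one-sided | At least one of 20 affected |
|---|---|---|---|
| 0 | 0.500 | 0.021 | 0% |
| 1% | 0.505 | 0.023 | 18% |
| 2% | 0.510 | 0.026 | 33% |
| 5% | 0.526 | 0.035 | 64% |
| 10% | 0.556 | 0.061 | 88% |

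If early failures stay in the 20, the value is 0.021 at every e.

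**The case against.** The strongest reply is that this is a missing cross-reference. Section 11.1.1 is the detailed definition, and 13.2 can be read as a short summary of it. Neither 13.2 nor 13.7.2 names progression or death, and 13.7.2 says who is eligible without saying that nobody else is. That is fair for 13.7.2 taken alone. It does not rescue 13.2, which makes one cycle a requirement and sets replacement and the decision rule beside it. The note in 11.1.1 is needed precisely because a one-cycle rule without it excludes early failures.

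Three further objections stand in part.

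- **The affected group is narrow.** Section 5.8 lets a participant who meets progression criteria but is judged to be benefiting continue therapy, and 11.1.2 requires reconfirmation when IgM is the only evidence of progression. A reader might infer that every Cycle 1 progressor is lost; the text supports this only for those who do not complete the cycle.
- **The proportion is probably small.** In the 63-patient ibrutinib-alone study described in 2.3, the earliest progression was at 3.5 months and 24-month survival was 95.2%. With a constant hazard over about 26 four-week periods, that is 1 − 0.952^(1/26), or about 0.2% mortality per cycle. Time on treatment in that study did start at 0.5 months, for a reason not given, and ulocuplumab was not part of it, so e for the combination remains unknown.
- **The inflation depends on what the null describes.** Section 13.2 states the null next to the evaluable patients. If it refers to them alone, the false-success probability is 0.021 whatever e is, but the rule then no longer speaks for everyone who started treatment.

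**Conclusion.** The conflict is real and confined to the 15/14 rule and the evaluable-set rate. Following 13.2 as written can turn a 14/20 failure into a 15/20 success by replacing one known non-responder. With the null read as applying to all treated participants, the false-success probability goes from 0.021 to 0.023 at an assumed e of 1% and 0.035 at 5%; the 0.061 at 10% needs an early failure rate that the cited ibrutinib-alone data do not suggest. At e = 0 there is no effect.

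Three stronger conclusions are not supported.

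- **That the primary response rate is biased upward.** The proportion that 13.5 calls primary is taken in the FAS, which keeps these participants in the denominator.
- **That the stated alpha is necessarily exceeded.** If 0.04 is read as one-sided, e must be above about 6% to pass it. If it is the doubled value, the comparison is with 0.021 one-sided.
- **That the trial's findings were affected.** Phase II never opened, so the rule was never applied. This is a defect of the written plan.

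**What to change.** In 13.2 and 13.7.2, replace the bare one-cycle condition with the 11.1.1 definition including its note. Participants who progress or die before the end of Cycle 1 are evaluable, count as non-responders among the 20 and are not replaced. Apply the 15/14 rule to that set. In 13.5, add a sentence on how the FAS proportion relates to it, since participants who leave in Cycle 1 for other reasons would still be in the FAS but not among the 20.

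The cost is one sentence in each of the three sections. It uses a definition the protocol already contains, and for this source of bias it keeps the design at its exact values (one-sided alpha 0.021, power 0.804). The downside is that the reported evaluable-set rate may be slightly lower.

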### 11.1.2 Response Criteria

**Complete Response (CR):** A complete response (CR) is defined as having resolution of WM related symptoms, normalization of serum IgM levels with complete disappearance of IgM paraprotein by immunofixation, and resolution of any adenopathy or splenomegaly. A complete response requires reconfirmation demonstrating normal serum IgM levels, and absence of IgM paraprotein by immunofixation by a measurement repeated at least 2 weeks later.

**Very Good Partial Response (VGPR):** is defined as  $\geq 90\%$  reduction in serum IgM levels, or normalization of serum IgM levels.

**Partial Response (PR):** Partial response (PR) is defined as achieving a  $\geq 50\%$  reduction in serum IgM levels.

**Minor Response (MR):** A minor response (MR) is defined 25-49% reduction in serum IgM levels.

**Progressive Disease (PD):** Progressive disease (PD) is defined as occurring when a greater than 25% increase in serum IgM level occurs with an absolute increase of at least 500 mg/dL from the lowest attained response value, or progression of clinically significant disease related symptom(s). Reconfirmation of the initial IgM increase is required when IgM is the sole criterion for progressive disease confirmation. Death from any cause or initiation of a new anti-neoplastic therapy will also be considered a progression event. For participants on active therapy who are on a drug hold for  $> 7$  days, serum IgM levels will be considered unevaluable for response assessment. Patient must be on study drug for  $> 2$  consecutive weeks to be considered eligible for serum IgM response assessment. An increase of 1 cm in any axis for adenopathy, or 2 cm in the craniocaudal axis of the spleen will be considered evidence of progression of extramedullary disease. Development of Bing Neel syndrome, or other extramedullary disease manifestations, as well as disease transformation will be considered as progressive events.

**Stable Disease (SD):** Stable disease is defined as having  $< 25\%$  change in serum IgM levels, in the absence of new or increasing adenopathy or splenomegaly and/or other progressive signs or symptoms of WM.

**Overall Response Rate (ORR):** Includes patients who achieved MR, PR, VGPR and CR.

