## **1.3 Secondary Objectives**

- Phase II: To determine the time to minor and major response, as well as time to progression (TTP) in symptomatic patients with CXCR4 mutated WM.
- Phase II: To determine the best overall response rate (ORR) (>25% reduction in disease burden) and Very Good Partial Response (>90% reduction in disease burden)/Complete Response (VGPR/CR) of ibrutinib combined with ulocuplumab in symptomatic patients with CXCR4 mutated WM.

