CT-defined adenopathy ( $\geq 1.5$  cm) was present in 37 patients at baseline. Serial imaging for 35 patients showed decreased or resolved (n=25; 67.6%); stable (n=9; 24.3%); or increased (n=1; n=2.9%) adenopathy. Two patients came off study before repeat imaging was required. Among 7 patients with CT-defined splenomegaly ( $\geq 15$  cm), spleen size was decreased (n=4; 57.1%), stable (n=2; 28.6%), or not evaluable (n=1; 14.3%) following elective splenectomy. Nine patients (14.3%), 3 with positive anti-MAG antibodies, received ibrutinib for progressive IgM-related peripheral sensory neuropathy. All responded, and subjective improvements in peripheral sensory neuropathy occurred in 5, and remained stable in 4 during the treatment course. Symptomatic hyperviscosity related to progressive disease that required plasmapheresis prompted start of ibrutinib in 4 patients. All responded, and none required additional plasmapheresis by the end of Cycle 2. One patient required plasmapheresis for acquired Factor VIII deficiency. He responded, and did not require further plasmapheresis. The spontaneous bleeding events that prompted therapy also resolved. With a median on treatment duration of 19.1 (range 0.5-29.7) months, 43 patients (68.3%) remained on therapy. Reasons for treatment discontinuation included non-response (n=1); progressive disease (n=7); treatment-aggravated thrombocytopenia (n=1); hematoma after BM biopsy (n=1); prolonged drug hold for infection unrelated to ibrutinib (n=1); myelodysplasia/acute myeloid leukemia associated with baseline 5q- deletion related to prior therapies (n=1); disease transformation possibly related to prior nucleoside analogue therapy (n=2); antineoplastic therapy for rectal carcinoma (n=1); ibrutinib incompatible medication (n=1), patient decision to use commercially sourced ibrutinib (n=2), travel difficulties (n=1), and alternative therapy (n=1). The estimated progression-free and overall survival at 24 months was 69.1% (95% CI 53.2%-80.5%) and 95.2% (95% CI 86.0-98.4%), respectively. For patients with progressive disease, the median time to progression was 9.6 (range: 3.5 – 19.4) months if transformation cases were censored, and 9.5 (range: 3.5 – 19.4) months if transformation events were included. Subset analysis showed that >3 prior lines of therapy, high pre-therapy IPSS score, and MYD88WTCXCR4WT mutation status associated with inferior progression-free survival.

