## **5.9 Duration of Follow Up**

Participants will be followed for up to 24 months after completion of protocol therapy, or until termination from study, disease progression, initiation of new anti-neoplastic therapy, or death. Participants removed from protocol therapy for unacceptable adverse event(s) will be followed until resolution of the adverse event to at least grade 1 or less, or stabilization of the adverse event. The Sponsor-Investigator has decided to terminate all follow-up as of 12/31/22.

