### **11.1.1 Time-to-event definition**

Progression-Free Survival (PFS) is defined as the duration of time from start of treatment to time of objective disease progression (including initiation of new therapy or death).

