### **13.6 Analysis of Secondary Endpoints**

The Per-Protocol Analysis Set (PPS) is defined as all participants from the FAS set who complete the study and are deemed to be protocol-compliant. To be protocol-compliant, a participant must not have any major protocol deviations during the study period. Protocol deviations will be identified prior to database lock and will be listed in the clinical study report. The PPS will be used for secondary assessment of efficacy endpoints.

Secondary analyses will be performed in both the FAS and PPS populations. There are no secondary endpoints for the Phase I portion of the protocol. For the Phase II participants the time to response, both major (PR or better) and minor response will be estimated using Kaplan Meier methodology with median time plus 25th and 75th percentile time to response along with 95% confidence intervals being provided, as appropriate. Time to progression (TTP) will also be estimated using Kaplan Meier methodology. Best overall response and Very Good Partial Response (>90% reduction in disease burden)/ CR (complete response) will be estimated in both

the FAS and PPS populations involving calculating the proportion of patients having an overall response (MR or better). Confidence intervals (95%) around these point estimates will be presented.

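### The Phase II endpoint labelled time to progression would have the events of PFS, because death and any new anti-neoplastic therapy count as progression

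*Combined protocol and SAP*

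**What the plan says.** - **Objective (Section 1.3).** For Phase II the secondary objectives include time to minor and major response, "as well as time to progression (TTP) in symptomatic patients with CXCR4 mutated WM".
- **Analysis (Section 13.6).** "Time to progression (TTP) will also be estimated using Kaplan Meier methodology". The section gives no time origin, event list, censoring rule or competing-risk rule for TTP. It also says that Phase I has no secondary endpoints.
- **Progressive disease rule (Section 11.1.2).** After the IgM and symptom criteria, the rule adds: "Death from any cause or initiation of a new anti-neoplastic therapy will also be considered a progression event". It then lists extramedullary progression and disease transformation as progressive events.
- **Time-to-event definition (the second of two sections numbered 11.1.1).** "Progression-Free Survival (PFS) is defined as the duration of time from start of treatment to time of objective disease progression", with new therapy and death included in brackets. This is the only time-to-event definition in the document. PFS for this trial does not appear in Sections 1.2, 1.3, 13.5 or 13.6.
- **Follow-up (Section 5.9, repeated in 13.2).** Participants are followed for up to 24 months after protocol therapy, "or until termination from study, disease progression, initiation of new anti-neoplastic therapy, or death".

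**The concern.** A reader of Sections 1.3 and 13.6 would expect TTP to measure when the WM progresses, with deaths and treatment changes that occur without progression handled separately. Section 11.1.2 makes both of them progression events, so the label and the quantity do not match.

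The therapy clause raises a second problem, which renaming alone would not cure. It covers any anti-neoplastic therapy, whatever cancer is being treated, and the protocol itself foresees second cancers. Section 7.1.1.2 lists non-melanoma skin cancer as a risk of ibrutinib and requires all new malignancies to be reported. Section 3.1.7 exempts topical treatment of basal cell and squamous cell skin cancers at entry, but Section 11.1.2 has no matching exemption. Read literally, treating such a cancer during the study would be scored as WM progression.

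At stake is what the secondary time-to-event estimate means and which published figures it could be set beside. Because TTP has no definition of its own, an analyst could also follow either the usual meaning of the name or the composite rule, and the plan does not settle which.

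**Working it through.** The plan states no TTP figure, event count or power, so there is nothing to reproduce. The check sets the definitions side by side.

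1. **Events if Section 13.6 is run with the progression rule of Section 11.1.2:** IgM progression, progression of clinically significant symptoms, extramedullary progression, transformation, death from any cause, and any new anti-neoplastic therapy.
2. **Events in the PFS definition of Section 11:** "time of objective disease progression (including initiation of new therapy or death". Objective progression takes its content from Section 11.1.2. The list is therefore the same, except that the PFS wording says new therapy without even the anti-neoplastic qualifier.
3. **Consequence.** If both are measured from the start of treatment (stated for PFS, not stated for TTP), and therapy is read the same way in both places, every participant has the same event time under either name. The two Kaplan-Meier curves coincide.
4. **Comparison with Section 5.9.** There, progression, new anti-neoplastic therapy and death are three separate reasons for ending follow-up. The protocol thus distinguishes them in one place and merges them in another.
5. **Can the unrelated-cancer case arise?** In the ibrutinib study summarised in Section 2.3, one of 63 participants stopped for "antineoplastic therapy for rectal carcinoma (n=1"). That shows such a case can occur. It gives no rate for this trial.
6. **Direction.** Scoring a death or a new therapy as an event, where a progression-only TTP would censor it, can only lower the Kaplan-Meier curve or leave it unchanged.
7. **Size, under assumptions only.** Suppose constant hazards, and that a share *s* of composite events are deaths or new therapies without progression. Then S(progression only) = S(composite)^(1 − *s*). For a starting value, borrow the 24-month PFS of 69.1% from the study in Section 2.3, treated for illustration as the composite:
   - *s* = 0: 69.1%
   - *s* = 10%: 0.691^0.90 = 71.7%
   - *s* = 25%: 0.691^0.75 = 75.8%
   - *s* = 50%: 0.691^0.50 = 83.1%

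   The documents give no value of *s* for this trial. The range shows only that the result depends on *s*; it is not an estimate.
8. **Link to follow-up.** Sections 5.9 and 13.2 end follow-up at any new anti-neoplastic therapy. If non-WM therapy stops being an event, those participants still leave observation on that date, so the text needs a censoring rule for them.

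**The case against.** The strongest reply is that the composite is openly stated. Section 11.1.2 lists its components, so the endpoint can be computed and a reader can see what it is; on this view only the name is wrong. The endpoint is also descriptive, with no hypothesis test, power calculation or decision rule attached. This largely stands, and it limits the point. It does not remove the point, for two reasons: Sections 1.3 and 13.6 carry a name that their own event rule contradicts, and scoring treatment of an unrelated cancer as WM progression is a fault of content, not of naming.

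Three stronger readings are tempting, and the documents do not support them.

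- **That the definition spoils comparison with the 9.6-month time to progression in Section 2.3.** That figure is a median among patients who progressed. The same study reports 24-month PFS of 69.1%, so 9.6 months cannot be a whole-cohort median. No Kaplan-Meier TTP over all treated participants would be comparable with it, however defined.
- **That the rule would raise the event count by some 22% to 33%.** One can get there from the same study by taking 9 progressions or transformations and adding 2 or 3 other discontinuations (2/9 = 22%, 3/9 = 33%). Those are reasons for stopping ibrutinib, not events under Section 11.1.2. The text does not say who later started new therapy, or that the one listed alternative therapy was anti-neoplastic. The count is neither an estimate nor a bound.
- **That a published TTP from this trial is wrong.** Sections 1.1 and 5.1 state that Phase II was not opened, and Section 13.6 gives Phase I no secondary endpoints.

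**Conclusion.** The point holds as a conditional comment on the plan: had Phase II run as written, the quantity labelled TTP would have been PFS with new therapy as an added event, including therapy for cancers other than WM. This follows from the text and needs no numerical assumption beyond the same time origin and the same reading of new therapy. The direction relative to a progression-only TTP is known (lower or equal); the size is not, and the documents offer no basis for one. Only a descriptive Phase II secondary endpoint is affected. The major response rate, the sample of 20 and its power do not depend on it. The text should still be corrected, because a stated rule gives the wrong quantity and the correction is cheap.

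**What to change.** Choose one of two routes.

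1. **Rename.** Call the endpoint PFS in Sections 1.3 and 13.6 and point to the time-to-event definition in Section 11. Renumber that section, since 11.1.1 is used twice, and align its new-therapy wording with Section 11.1.2.
2. **Define TTP separately.** State the time origin. The event is disease progression or transformation. Death without progression is censored or treated as a competing event; if competing, Section 13.6 should name a cumulative incidence estimate in place of Kaplan-Meier. New therapy without progression is censored at its start. Death and new therapy then count as events for PFS only.

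On either route, wherever new anti-neoplastic therapy is an event, limit it to therapy for WM. State that participants who start anti-neoplastic therapy for another cancer are censored on that date, which matches the end of follow-up in Sections 5.9 and 13.2.

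The cost is a few sentences in Sections 1.3, 11 and 13.6. With censoring at the start of non-WM therapy, no extra follow-up or data are needed. As Phase II was not opened, the change matters if TTP is ever described for the enrolled participants or if this text is reused.
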